3.1 General Description

This is a single center, exploratory, open-label, single-arm design study of 12 patients. Treatment naïve and treatment refractory patients with LP will be treated Baricitinib (LY3009104). Patients who are non-responders to physician choice standard of care will undergo a washout period and will be enrolled in the study.

Multiple safety studies have been conducted with Baricitinib (LY3009104) (see Safety) and a dose of 2 mg QD is deemed safe. (Investigator's Brochure) We propose a single center, exploratory, open-label, single-arm design study of 12 patients. Treatment naïve and treatment refractory patients with LP will be treated with Baricitinib (LY3009104) for 16 weeks.

Individuals with cutaneous LP will be eligible. Individuals must have 4 lesions at baseline; however, a minimum of 8 lesions which are at least 5mm in diameter is ideal. All lesions will be annotated, photographed, and scored. The rationale for a minimum of 8 lesions is based upon the assumption of a 50% response rate at 2 weeks. With 8 lesions, there would be a less than 1% chance that all 8 lesions would resolve spontaneously. Prior treatment will be allowed; however, a washout period of 2 weeks for topical and 4 weeks for systemic agents is required. At the washout period, individuals will undergo evaluation with a PGA and BSA calculation. The indexed lesions will be photographed, measured, scored, and recorded with Modified CAILS scores as well. The Modified CAILS calculations will be used for the determination of responsive and non-responsive lesions. Additional Pruritus measures using the VRS, VAS, NRSSkindex-16, and LPQOL will be collected at that time.

Individuals will then initiate treatment for all lesions of LP once daily and will be evaluated weekly and assessed by PGA of skin, oral mucosa, and hair, BSA, lesion count, Modified CAILS, Pruritus VRS, VAS and NRS scales, Skindex-16, and LPQOL between weeks 0-16 (see Appendix). Week 16 will be the primary endpoint. Therapy will be stopped and the individuals will be evaluated at week 20 after an observation period of 4 weeks and assessed by PGA, BSA, lesion count, mCAILS, Pruritus VRS, VAS and NRS scales, Skindex-16, and LPQOL. Laboratory and safety monitoring will occur at weeks 1, 2, 3, 4, 8, 12, 16, 20, 24, 28, and 32. 3D Photographs will be taken at weeks 0, 1, 2, 3, 4, 8, 12, 16, 20, 24, 28, and 32. Individual lesions will be circled at each visit and the exact area of each lesion will be measured. Up close photos will be taken of the disease.

week 0 and 2. Blood collection will include the isolation at week 0, 1, 2, 3, 4, 8, 12, 16, 20, 24, 28, and 32. Blood will be drawn into 5mL vials and subsequently separated. The serum and cell pellet will be stored for future analysis. At weeks 0 and 2, an additional 5mL vial of blood will be drawn from patients who agree to provide single-cell RNA sequencing samples. For these samples, the buffy coat (containing peripheral blood mononuclear cells, PBMCs) will be isolated from whole blood, then immediately placed into cryopreservation medium and stored in a -80°C biobank freezer. Up to five skin biopsies will be taken during the study for all patients. At week 0, up to two, 3mm tissue biopsies will be taken from LP lesional skin and one biopsy will be taken from normal appearing skin for bulk RNA sequencing. The initial biopsy of lesional tissue and control will be annotated. At week 2, up to two, 3mm biopsies will be taken – one from normal appearing skin, one from lesional responsive tissue, and/or one from lesional non-responsive tissue. An additional two, 6-8mm biopsies of lesional tissue for single-cell RNA sequencing will be taken—one at week 0 and one at week 2 from patients who opt in. The week 2 biopsy will be obtained from an annotated lesion, whether responsive or non-responsive. Responsive and non-responsive lesions will be determined by the change in mCAILS between week 0 and 2. Responsive tissue will require at least 50% reduction in mCAILS while non-responsive tissue can have progression, no change, or up to a 50% reduction in mCAILS. The lesions will be chosen utilizing full body photographs taken previously at week 0. Up to 60 of the 3mm biopsy samples will be snap frozen and stored in the tissue biobank. Once completed, RNA sequencing will be performed on the tissue samples and analysis will be performed. Paired analysis of treatment responsive and refractory lesions will be made as well as treated and untreated lesions.

Tissue will be collected for bulk RNA sequencing and single cell RNA sequencing (for patients who opt in) at

Nucleic Acid Extractions: RNA will be extracted from a total of 50 µm of fresh tissue using the Qiagen FFPE RNeasy Micro extraction Kit according to manufacturer's recommendation.

Bulk RNA Transcriptome Sequencing: RNA transcriptome sequencing will be carried out using commercially available techniques. Briefly, RNA Libraries will be created using up to 100ng of RNA as starting material using the Illumina RNA Exome Library kit according to manufacturer's recommendation. Libraries will undergo quality control for quality and quantity using the Agilent BioAnalyzer High Sensitivity Chip. Pair-End sequencing will then be carried out on the Illumina HiSeq 4000 using 101bp insert fragments.

Single-cell RNA Transcriptome Sequencing: Samples will be prepped and analyzed per single-cell RNA sequencing standard operating procedures of the University of Michigan genomics lab.

Primary and Secondary Measures:

All efficacy assessments will be performed prior to the administration of study treatment at each visit. The recommended order and the overall outline of measurements for the efficacy assessments are described below.

Efficacy measures: PGA, BSA, mCAILS, Pruritus VRS, VAS and NRS, Skindex-16, and LPQOLto determine the efficacy of Baricitinib (LY3009104) as measured by the change in Modified CAILS score of the index lesion (weeks 0 and 16) and changes in lesion count (week 0 and 16).

Secondary Outcome Measures: To determine the efficacy of Baricitinib (LY3009104) as measured by the change in Pruritus VAS, VRS, & NRS, (week 0 to week 2, weeks 0 to 4, weeks 4 to 8, weeks 0 to 8, weeks 8 to 12, weeks 0 to 12, weeks 12 to 16, weeks 0 to 16, weeks 16 to 20, weeks 0 to 20, weeks 0 to 24, week 20 to 24, week 0 to 28, weeks 24 to 28, weeks 0 to 32, week 28 to 32), change in Skindex-16 (week 0 to week 2, weeks 0 to 4, weeks 0 to 20, weeks 0 to 20, weeks 0 to 12, weeks 12 to 16, weeks 0 to 16, weeks 16 to 20, weeks 0 to 20, weeks 0 to 24, week 20 to 24, week 0 to 28, weeks 0 to 8, weeks 8 to 12, weeks 0 to 32, week 28 to 32), change in LPQOL (week 0 to week 2, weeks 0 to 4, weeks 4 to 8, weeks 0 to 8, weeks 8 to 12, weeks 0 to 12, weeks 12 to 16, weeks 0 to 16, weeks 16 to 20, weeks 0 to 20, weeks 0 to 24, week 20 to 24, week 0 to 28, week 24 to 28, weeks 0 to 32, week 28 to 32), change in Physician Global Assessment (PGA) of skin, oral mucosa, and hair (week 0 to week 2, weeks 0 to 4, weeks 4 to 8, weeks 0 to 8, weeks 8 to 12, weeks 0 to 12, weeks 12 to 16, weeks 0 to 16, weeks 16 to 20, weeks 0 to 20, weeks 0 to 24, week 20 to 24, week 0 to 28, week 24 to 28, weeks 0 to 32, week 28 to 32), change in BSA (week 0 to week 2, weeks 0 to 4, weeks 0 to 4, weeks 0 to 20, weeks 0 to 20, weeks 0 to 20, weeks 0 to 20, weeks 0 to 32, weeks 0 to 32, week 28 to 32), change in BSA (week 0 to week 2, weeks 0 to 4, weeks 0 to 20, weeks 0 to 8, weeks 0 to 4, weeks 0 to 12, weeks 0 to 12, weeks 0 to 16, weeks 0 to 16, weeks 0 to 16, weeks 0 to 12, weeks 0 to 16, weeks 0 to 12, weeks 0 to 16, weeks 0 to 20, weeks 0 to 16, weeks 0 to 1

weeks 0 to 24, week 20 to 24, week 0 to 28, week 24 to 28, weeks 0 to 32, week 28 to 32), change in Modified CAILS (week 0 to week 2, weeks 0 to 4, weeks 4 to 8, weeks 0 to 8, weeks 8 to 12, weeks 0 to 12, weeks 12 to 16, weeks 16 to 20,weeks 0 to 20,weeks 0 to 24, week 20 to 24, week 0 to 28, week 24 to 28, weeks 0 to 32, week 28 to 32), and change in lesion count (week 0 to week 2, weeks 0 to 4, weeks 4 to 8, weeks 0 to 8, weeks 8 to 12, weeks 0 to 12, weeks 12 to 16, weeks 16 to 20,weeks 0 to 20,weeks 0 to 24, week 20 to 24, week 0 to 28, week 24 to 28, weeks 0 to 32, week 28 to 32).

Exploratory Outcome Measures: To predict responses and examine the pharmacodynamics of treatment through the identification of unique biomarkers and transcriptomic changes of LP at week 0, and utilizing RNA sequencing on responsive and non-responsive tissue at week 2 to correlate these biomarkers with measures of global response: Modified CAILS, PGA, BSA, and lesion count.

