Objectives	To evaluate the safety and efficacy of Baricitinib (LY3009104) in cutaneous LP as assessed by the change in Physician Global Assessment (PGA) of skin, oral mucosa, and hair, Body Surface Area (BSA), Index Treatment and Control Lesion by Modified Clinical Assessment Scale of Severity for Index Lesion Signs and Symptoms (mCAILS) score, Pruritus Visual Analog Scale (VAS), Verbal Rating Scale (VRS), Pruritus Numerical Rating Scale (NRS), and Skindex-16. To predict responses through the identification of unique biomarkers of LP at week 0 and utilizing RNA sequencing on responsive and non-responsive tissue at week 2.						
Number of Subjects	12						
Diagnosis and Main Inclusion Criteria	Non-pregnant adults with cutaneous LP						
Study Product, Dose, Route, Regimen	Baricitinib (LY3009104) 2 mg orally administrated, once daily.						
Duration of Administration	Drug will be administered from Day 0 through Week 16.						
Reference therapy	Baricitinib (LY3009104) is currently being used to treat subjects with rheumatoid arthritis and under investigation for atopic dermatitis and psoriasis.						
Statistical Methodology	The statistical analysis will provide descriptive summary statistics for categorical and continuous outcomes. Categorical variables will be described by their count and proportion of occurrence while continuous, normally distributed variables will be described by their mean and standard deviation; and continuous, non-normally distributed variables will be described by their median and range						

1 Introduction

This document is a protocol for a human research study. This study will be carried out in accordance with the applicable United States government regulations and Mayo Clinic research policies and procedures.

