1.5 Dose Rationale

Balancing the safety risks and efficacy data of varying baricitinib doses from prior studies, our study proposes oral Baricitinib (LY3009104) 2 mg QD dosing for 16 weeks (primary endpoint) in LP study subjects. If the patient opts into the extension portion of the study, the dose will escalate to 4 mg.

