3.3 Duration of Participation

The study consists of 3 epochs: screening/washout period (at least 1 week and up to 4 weeks), treatment epoch (16 weeks from screen/washout), and follow up epoch (4 weeks). The screening and washout period will allow for treatment naïve/ new diagnosis LP to undergo evaluation and diagnosis and for treatment refractory to undergo a washout. The total duration of the study will be 21-24 weeks, with the option to enroll in a 3 month extension with a dose escalation to 4 mg for patients who demonstrate response to treatment, but have not yet achieved PGA 0

Tables:

Table-1: Prohibited treatment

Prohibited treatments ^{†,‡}	Washout period (before Randomization Visit)
Any concomitant oral or topical JAK inhibitor	Prohibited
Any biologic drug	Stable dose for 3 months
Immunomodulation treatments for LP§	4 weeks
[e.g., methotrexate, cyclosporine A, corticosteroids (oral, i.v.,	
intramuscular, s.c., intra-articular, transdermal),	
mycophenolate mofetil, azathioprine]	
Topical treatment that is likely to impact signs and symptoms of LP (e.g., pimecrolimus, tacrolimus)	2 weeks
Non-immunosuppressive agents (tetracycline antibiotics & niacinamide)	2 weeks
Prohibited regimen of Topical Corticosteroids (TCS)	
TCS on any location on body (including face, scalp and/or genitoanal area)	2 weeks

[†]If the prohibited treatment is being used during the study for any indication, the subject must discontinue use of the prohibited treatment if he/she wishes to continue in the study.

[‡] In case of undue safety risk for the subject, the subject should discontinue study treatment at the discretion of the investigator/qualified site staff. If the subject received a live virus vaccination during the study, the subject must discontinue study treatment.

§Inhalative CS with only a topical effect (e.g., to treat asthma) are not considered "systemic immunomodulation treatments" and are therefore acceptable as co-medication. Immunosuppressive medication for conditions other than LP will be allowed.

Table 2: Washout Periods for Monoclonal Antibodies (Biologic Drugs)

Brand	Generic Name	Recommended Minimum
Name		Washout (approximately 5 half-lives)
ACTEMRA	Tocilizumab	8 weeks
CIMZIA	Certolizumab pegol	10 weeks
COSENTYX	Secukinumab	16 weeks
DUPIXENT	Dupilumab	12 weeks
ENBREL	Etanercept	4 weeks
HUMIRA	Adalimumab	8 weeks
KEVZARA	Sarilumab	7 weeks
ORENCIA	Abatacept	8 weeks
REMICADE	Infliximab	6 weeks
RITUXIN	Rituximab	6 months
SIMPONI	Golumimab	10 weeks

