5.2 Treatment Regimen

Subjects will administer Baricitinib (LY3009104) 2 mg tablet once daily on an empty stomach. Treatment will take place from Day 0 to Week 16.

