5.3 Preparation and Administration of Study Drug

The study drug will be supplied by Eli Lilly to the Mayo Clinic Pharmacy, attn. [name], Pharm D, R.Ph. [name]. The study drug will be stored in the Mayo Clinic Pharmacy. The study drug will be labelled in the Mayo Clinic Pharmacy and will be dispensed to the subjects. The subjects will be given sufficient quantity of tablets at each visit for use between subsequent study visits. Instructions on proper use will be provided to each subject.

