5.7.3 Dispensing of Study Drug

Regular study drug reconciliation will be performed to document drug assigned, drug dispensed, drug returns, and drug remaining. This reconciliation will be logged on the drug reconciliation form and signed and dated by the study team. A three month extension and dose excalation to 4mg will be available to all patients who demonstrate response to treatment, but have not yet achieved PGA 0

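### Drug use after Week 16 is contradictory and the extension has no start week; if it starts at Week 16, the Week 20 changes would by default mix off-drug and 4 mg patients

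*Combined protocol and SAP*

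**What the plan says.** **Stop at Week 16.** The Study Summary says "Drug will be administered from Day 0 through Week 16", and Section 5.2 says "Treatment will take place from Day 0 to Week 16". Section 3.1 makes Week 16 the primary endpoint and continues: "Therapy will be stopped and the individuals will be evaluated at week 20 after an observation period of 4 weeks". It makes no exception for extension patients. Section 3.3 describes a "treatment epoch (16 weeks from screen/washout), and follow up epoch (4 weeks").

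**Extension.** Section 1.5 says "If the patient opts into the extension portion of the study, the dose will escalate to 4 mg". Section 3.3 offers a "3 month extension with a dose escalation to 4 mg for patients who demonstrate response to treatment, but have not yet achieved PGA 0". Section 5.7.3 repeats that it "will be available to all patients who demonstrate response to treatment, but have not yet achieved PGA 0". Section 2 extends observation to Week 32 for patients who choose the extension. None of these sections gives a start week.

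**Supply.** The baricitinib row of Table 3 is marked at Weeks 16, 20 and 24 and blank at Weeks 28 and 32. The visit lists agree: drug is dispensed at Visits 9, 10 and 11 (Weeks 16, 20 and 24) and not at Visits 12 and 13. No entry is marked as extension only. Section 5.3 adds: "The subjects will be given sufficient quantity of tablets at each visit for use between subsequent study visits".

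**Analysis.** Section 3.5 lists 16-20 and 0-20 changes for the itch scales, Skindex-16, LPQOL, PGA of oral mucosa and hair, BSA, mCAILS and lesion count, and further windows to Week 32. Section 7.3 defines one population, everyone who took at least one dose. Section 7.2 has no stratum or model term for treatment after Week 16.

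**The concern.** The plan cannot be followed as written after Week 16. A patient whose therapy has stopped under Section 3.1 is, under Table 3 and the visit lists, given drug at Weeks 16 and 20.

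The consequence for the analysis depends on the missing start week. If escalation begins at Week 16, some patients at Week 20 are four weeks off drug and others are on 4 mg. Membership is not random. Under Sections 3.3 and 5.7.3 the extension takes responders short of PGA 0 who opt in, which leaves patients at PGA 0, non-responders and those who decline in the stopped group. A pooled 16-20 or 0-20 change would then describe neither the course after stopping nor the course on 4 mg. Section 7.2 says the 12-patient study exists to give estimates for planning later studies, so each estimate needs a known treatment state behind it.

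**Working it through.** The point rests on no power or error-rate figure. The check is timeline and supply arithmetic, followed by a comparison of sections.

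**1. The plan's own duration.** Screening or washout lasts 1 to 4 weeks, treatment 16 and follow-up 4 (Section 3.3). 1 + 16 + 4 = 21 and 4 + 16 + 4 = 24 weeks. The stated 21 to 24 weeks reproduces, with the core study ending at Week 20.

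**2. The payment total.** Section 12.2 pays $50 for each of two biopsy visits and $25 for every other visit, $300 in all. The 10 visits from screening to Week 20 give 2 x 50 + 8 x 25 = $300. All 13 visits in Table 3 would give 2 x 50 + 11 x 25 = $375. So the stated total for completing all visits stops at Week 20. This does not date the extension, but it suggests that the extension was not carried through the whole text.

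**3. Candidate start weeks.** Three months is taken as 12 weeks (84 days), and each dispensing visit is taken to supply the interval to the next visit (28 days here).

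| | Start at Week 16 | Start at Week 20 |
|---|---|---|
| End of 12 weeks | 16 + 12 = Week 28 | 20 + 12 = Week 32 |
| Extension supply from marked visits | Weeks 16, 20, 24: 3 x 28 = 84 days | Weeks 20, 24: 2 x 28 = 56 of 84 days |
| Weeks left before Week 32 | 4 | 0 |
| Stop and Week 20 evaluation (Section 3.1) | Conflicts | Fits |
| Dispensing at Week 16 | Fits | Unexplained |
| No dispensing at Week 28 | Fits | Last 4 weeks unsupplied |

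No start week satisfies every section. Taking three months as 13 weeks moves the ends to Weeks 29 and 33 and removes neither conflict.

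**4. What this does to the Week 20 changes.** Under a Week 16 start, patients are in two treatment states at Week 20. Section 3.5 does not restrict the 16-20 and 0-20 changes to either group, and Sections 7.2 and 7.3 supply no split, so the default summary combines them. Under a Week 20 start, everyone has stopped for four weeks and there is one state.

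**5. Would both states occur among 12 patients?** The documents give no entry rate, so this is an assumption. If each of 12 patients independently enters with probability p, the chance that both states are present is 1 - p^12 - (1 - p)^12. This is 72% for p = 0.10 or 0.90, 93% for p = 0.20, 97% for p = 0.25 or 0.75, and above 99.9% for p = 0.50. It applies only under a Week 16 start and says nothing about how far the pooled figure would be off.

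**6. What is untouched.** Section 3.1 places efficacy assessments before dosing at each visit. The Week 16 assessment therefore precedes any change of treatment made at that visit, and the primary endpoint and all windows ending by Week 16 stand.

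**The case against.** The strongest reply is that the mixture needs two things the documents do not state: a Week 16 start and a pooled summary. Section 3.1 stops therapy without exception, Section 2 ends its general windows at Week 20, Week 20 plus 12 weeks reaches Week 32, and the payment total also ends at Week 20. On that reading nothing is mixed. Section 7.3 says who is considered for analysis; it does not order an average across treatments. This stands as a limit on the consequence. It does not remove the contradiction, because a Week 20 start still leaves the Week 16 dispensing unexplained and nothing dispensed at Week 28.

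A reader might infer more than the text supports in three places:

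- *That the Weeks 24-32 windows are presented as all-patient results.* Section 3.5 does not say whom they describe, but Section 2 ties observation to Week 32 to patients who choose the extension. What remains is to label them and give the number of patients.
- *That a definite share of the Section 3.5 changes turns on the missing date.* No clean count exists. The starting state of the 20-24 change also depends on the date. Week 32 does not depend on it alone: with nothing dispensed at Week 28, that visit is off drug under either start, unless the three-month length overrides the dispensing schedule.
- *That the last-observation-carried-forward analysis in Section 7.2 would carry values across the change of treatment.* The section does not say so, and visits not scheduled for a patient need not count as missing.

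**Conclusion.** The contradiction is established from the text: three places end treatment at Week 16, Table 3 and the visit lists dispense drug afterwards without an extension label, and no section says when the extension starts. This should be fixed however the extension was intended to run.

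The effect on the analysis is conditional. It requires a Week 16 start, at least one patient in each state, and the default of one population with no split. If all three hold, the 16-20 and 0-20 changes in each endpoint group of Section 3.5 describe a response-selected mixture. The documents give neither the number who would escalate nor the effects of stopping or escalating, so the distortion cannot be sized. It would be wrong to say that the Week 20 results are mixed as planned.

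The matter is moderate. The endpoints at risk are secondary and descriptive, in a 12-patient study meant for estimation only.

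**What to change.** **Protocol.** Reconcile the Study Summary, Sections 1.5, 3.1, 3.3, 5.2 and 5.7.3, Table 3 and the Week 16, 20 and 24 visit lists on drug use after Week 16. State when the extension starts and ends, and mark which dispensing entries apply to extension patients only. No view is taken here on which rule is right.

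**Analysis plan.** Pool all patients only through Week 16. From Week 20, report stopped and extension patients separately, with the treatment state at each visit. Label the Weeks 24-32 windows as extension patients only, in line with Section 2, and give their number.

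**Cost.** Wording changes only, since the assessments are already in Table 3. The drawback is very small groups after Week 16, so individual patient profiles may be all that can usefully be shown.

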3.2 Number of Subjects

12 subjects will be enrolled in this study.

3.3 Duration of Participation

The study consists of 3 epochs: screening/washout period (at least 1 week and up to 4 weeks), treatment epoch (16 weeks from screen/washout), and follow up epoch (4 weeks). The screening and washout period will allow for treatment naïve/ new diagnosis LP to undergo evaluation and diagnosis and for treatment refractory to undergo a washout. The total duration of the study will be 21-24 weeks, with the option to enroll in a 3 month extension with a dose escalation to 4 mg for patients who demonstrate response to treatment, but have not yet achieved PGA 0

Tables:

Table-1: Prohibited treatment

Prohibited treatments ^{†,‡}	Washout period (before Randomization Visit)
Any concomitant oral or topical JAK inhibitor	Prohibited
Any biologic drug	Stable dose for 3 months
Immunomodulation treatments for LP§	4 weeks
[e.g., methotrexate, cyclosporine A, corticosteroids (oral, i.v.,	
intramuscular, s.c., intra-articular, transdermal),	
mycophenolate mofetil, azathioprine]	
Topical treatment that is likely to impact signs and symptoms of LP (e.g., pimecrolimus, tacrolimus)	2 weeks
Non-immunosuppressive agents (tetracycline antibiotics & niacinamide)	2 weeks
Prohibited regimen of Topical Corticosteroids (TCS)	
TCS on any location on body (including face, scalp and/or genitoanal area)	2 weeks

[†]If the prohibited treatment is being used during the study for any indication, the subject must discontinue use of the prohibited treatment if he/she wishes to continue in the study.

[‡] In case of undue safety risk for the subject, the subject should discontinue study treatment at the discretion of the investigator/qualified site staff. If the subject received a live virus vaccination during the study, the subject must discontinue study treatment.

§Inhalative CS with only a topical effect (e.g., to treat asthma) are not considered "systemic immunomodulation treatments" and are therefore acceptable as co-medication. Immunosuppressive medication for conditions other than LP will be allowed.

Table 2: Washout Periods for Monoclonal Antibodies (Biologic Drugs)

Brand	Generic Name	Recommended Minimum
Name		Washout (approximately 5 half-lives)
ACTEMRA	Tocilizumab	8 weeks
CIMZIA	Certolizumab pegol	10 weeks
COSENTYX	Secukinumab	16 weeks
DUPIXENT	Dupilumab	12 weeks
ENBREL	Etanercept	4 weeks
HUMIRA	Adalimumab	8 weeks
KEVZARA	Sarilumab	7 weeks
ORENCIA	Abatacept	8 weeks
REMICADE	Infliximab	6 weeks
RITUXIN	Rituximab	6 months
SIMPONI	Golumimab	10 weeks
STELARA	Ustekinumab	16 weeks
TALTZ	Ixekizumab	10 weeks
TREMFYA	Guselkumab	12 weeks
XOLAIR	Omalizumab	16 weeks

Table-3: Screening and Visits (+/- 3-day window)

	Screening	Day 0	Week 1	Week 2	Week 3	Week 4	Week 8	Week 12	Week 16	Week 20	Week 24	Week 28	Week 32
Baricitinib (LY3009104)		Х	Х	х	х	Х	Х	Х	Х	Х	Х		
Physical Exam	Х	Х	Х	Х	Х	Х	Х	Х	Х	Х	Х	Х	Х
Adverse Event Assessment		Х	Х	Х	Х	Х	Х	Х	Х	Х	Х	Х	Х
Chest X-ray	Х												
Assessments: PGA, BSA, lesion number, mCAILS, Skindex-16, Pruritus VAS, VRS & NRS, LPQOL		х	х	х	х	х	х	х	х	х	Х	Х	Х
Photographer		Х	х	Х	Х	x	x	x	х	X	Х	Х	Х
Skin Biopsy (tissue/serum bank)		Х		Х									
ECG	Х					Х							
Urine Pregnancy Test	Х	Х				Х	Х	Х	Х	Х	Х	Х	Х
Venipuncture	Х	Х	Х	Х	Х	Х	Х	Х	Х	Х	Х	Х	Х
Biomarker/RNAseq blood (tissue/serum bank)		Х	х	Х	x	х	х	х	х	х	Х	Х	Х
CMP	Х		Х	Х	Х	Х	Х	Х	Х	Х	Х	Х	Х
Lipid Panel	Х		Х	Х	Х	Х	Х	Х	Х	Х	Х	Х	Х
СРК	Х		Х	Х	Х	Х	Х	Х	Х	Х	Х	Х	Х
CBC	Х		Х	Х	Х	Х	Х	Х	Х	Х	Х	Х	Х
Quantiferon Gold	Х												
Hepatitis B	Х												
Hepatitis C	Х												

HIV	Х						
Coccidioidomycosis	Х						

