3.4 Primary Study Endpoints

Overall response by PGA of skin at week 16.

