Appendix:

Physician Global Assessment: 17, 18

Grade 0 Completely clear: no evidence of disease (100% improvement) CCR

Grade 1 Almost clear: very significant clearance (≥90% to <100%) PR

Grade 2 Marked Improvement: significant improvement (≥75% to <90%) PR

Grade 3 Moderate improvement: intermediate between slight and marked (≥50% to <75%) PR

Grade 4 Slight improvement: some improvement (≥25% to <50%); however, significant evidence of disease remains SD

Grade 5 No change; disease has not changed from baseline condition (+/-<25%) SD

Grade 6 Worse, disease is worse than at baseline evaluation by (≥25%) or more PD

CCR- Complete clinical response

PR- Partial response

SD- Stable disease

PD- Progressive Disease

Modified CAILS-

Clinical Assessment Scale of Severity for Index Lesion Signs and Symptoms (mCAILS) 17,18

Scale Grade

- 0 No evidence of sign or symptom
- 1 Intermediate interval
- 2 Mild: less than average presentation of sign or symptom
- 3 Intermediate interval
- 4 Moderate: average disease presentation of sign or symptom
- 5 Intermediate interval
- 6 Severe: greater than 25% worse than average severity of sign or symptom
- 7 Intermediate interval
- 8 Very severe: the near worst severity sign or symptom

A scale of 0 to 18 was used to grade lesion size by square centimeter (0, 0 [no measurable area]; 1, >0 and \leq 4; 2, >4 and \leq 10; 3, >10 and \leq 16; 4, >16 and \leq 25; 5, >25 and \leq 35; 6, >35 and \leq 45; 7, >45 and \leq 55; 8, >55 and \leq 70; 9, >70 and \leq 90; 10, >90 and \leq 110; 11, >110 and \leq 130; 12, >130 and \leq 15; 13, >155 and \leq 180; 14, >180 and \leq 210; 15, >210 and \leq 240; 16, >240 and \leq 270; 17, >270 and \leq 300; and 18, >300). The area of the lesion will be measured with digital planimetry. 17-19

mCAILS index lesion score:

- 1. Erythema (0-8)
- 2. Scaling (0-8)
- 3. Plaque elevation (0-8)
- 4. Size (0-18)
- o Trained clinical evaluators assessed the same patients throughout the study.
- o The CA (the ratio of summation (Σ) of all clinical signs for these index lesion at each visit compared with baseline) included cutaneous tumors and all extra cutaneous manifestations of disease.
- o Complete clinical remission (CCR) required a CA ratio of 0 with no evidence of disease
- o Partial remission (PR) was defined as a CA ratio of 0.5 or lower
- o Progressive disease was defined as a 25% or higher increase in CA ratio (Olsen et al., 2011b, Duvic et al., 2001b)

Itch-

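### Unmasked visits list clinician grading before patient self-rating, and the Week 16 PGA appears to inform extension entry as well as the primary endpoint; reordering and locking would cheaply limit both routes for bias

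*Combined protocol and SAP*

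**What the plan says.** **Design.** Section 3.1: "This is a single center, exploratory, open-label, single-arm design study of 12 patients". No masked or independent rater is named. Section 3.6 asks that, where possible, one staff member assess a given subject throughout.

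**Primary endpoint.** Section 3.4: "Overall response by PGA of skin at week 16". The grades that count as response are not listed there. The appendix grades the PGA as percentage improvement from baseline and attaches labels: grade 0 is CCR, grades 1 to 3 are PR, grades 4 and 5 are SD, and grade 6 is PD. The lowest PR grade reads "Grade 3 Moderate improvement: intermediate between slight and marked (≥50% to <75%) PR".

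**Extension.** Section 3.3 offers it "for patients who demonstrate response to treatment, but have not yet achieved PGA 0", and section 5.7.3 repeats that it "will be available to all patients who demonstrate response to treatment, but have not yet achieved PGA 0". Section 1.5 adds: "If the patient opts into the extension portion of the study, the dose will escalate to 4 mg". None of the three gives a PGA cut-off or says who judges response. Table 3 and the visit descriptions have drug dispensed at Weeks 16, 20 and 24, so the extension appears to begin at the primary-endpoint visit.

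**Order of assessments.** Under the primary and secondary measures, section 3.1 states: "The recommended order and the overall outline of measurements for the efficacy assessments are described below". The list that follows begins "Efficacy measures: PGA, BSA, mCAILS, Pruritus VRS, VAS and NRS, Skindex-16" and ends with LPQOL. Table 3 also names the clinician scales before the patient scales. The visit checklists open with physical and lesion examination and contain no questionnaire step.

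**The concern.** Two features of the visit leave room for expectation to enter the data, in a trial with no control arm to offset it.

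The first is sequence. A patient who has just been examined and graded may have picked up the clinician's view before marking an itch line or answering a quality-of-life item. Change from baseline does not reliably cancel this: at Day 0 there is no improvement to convey, whereas at later visits there may be.

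The second is double use of one judgement. The Week 16 PGA is subjective and unmasked, and it appears to feed a decision in which patient and clinician may both have a stake. Nothing requires the grade to be recorded before that decision is discussed.

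At stake is the estimate, not a type I error. Sections 7.1 and 7.2 say the effect sizes from this study will inform power and sample size for later trials. An estimate that is too favourable would make those trials too small.

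**Working it through.** The plan gives no expected response rate and no figure for measurement error, so it has no number of its own to reproduce on this point. The sample sizes in section 7.1 concern power and play no part.

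**1. Which way could the extension condition pull?** Assume that response in sections 3.3 and 5.7.3 means the appendix's CCR or PR. Then:

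| PGA grade | Appendix label | Counts in CCR+PR | Meets extension condition |
|---|---|---|---|
| 0 | CCR | yes | no (PGA 0 reached) |
| 1, 2, 3 | PR | yes | yes |
| 4, 5 | SD | no | no |
| 6 | PD | no | no |

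- At the 3/4 boundary (50% improvement), grade 3 meets the condition and grade 4 does not. A shift from 4 to 3 adds one to CCR+PR.
- At the 0/1 boundary, grade 1 meets the condition and grade 0 does not. A shift from 0 to 1 removes one from CCR and adds one to PR, so CCR+PR is unchanged.

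Now suppose instead that slight improvement (grade 4) is enough. The boundary moves to grade 4 against grade 5. Both are SD, so a shift there leaves CCR+PR untouched. The effect on the primary result therefore depends on a definition the protocol does not give.

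**2. What is one patient worth?** With n = 12 (section 3.2), 1/12 = 8.3 percentage points. Illustration with exact (Clopper-Pearson) 95% intervals; the starting count of 4 is assumed:

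- 4/12 = 33.3% (9.9 to 65.1)
- 5/12 = 41.7% (15.2 to 72.3)
- 6/12 = 50.0% (21.1 to 78.9)

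Two patients moved from grade 4 to grade 3 shift the estimate by 2 × 8.3 = 16.7 points, well inside either interval but large as a planning input.

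**3. Expected bias under assumed misgrading.** Let p be the true response proportion and m the share of true non-responders graded as responders, with no error the other way. The expected upward bias is (1 − p) × m.

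- p = 0.6, m = 0.1: 0.4 × 0.1 = 0.04, or 4 points
- p = 0.3, m = 0.3: 0.7 × 0.3 = 0.21, or 21 points

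The documents give neither p nor m, so 4 to 21 points is the range over those assumptions, not an estimate.

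**4. Itch and quality of life.** No calculation is possible. Section 3.1 recommends the order, but no section says patients are told their grade, and no figure supports either a size or a direction.

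**5. Would mCAILS and BSA serve as an independent check?** The mCAILS maximum is 8 + 8 + 8 + 18 = 42. Erythema, scaling and elevation, 24 of the 42 points, are graded by the same unmasked staff. Size uses digital planimetry, but size score 1 covers every lesion above 0 and up to 4 cm², a circle about 2 × √(4/π) = 2.26 cm across. For small lesions the size item stays at 1 until clearance. These measures can show consistency with the PGA; they cannot remove the bias.

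**The case against.** A reader might infer that the protocol builds in one-directional inflation of both the primary and the itch results. The documents do not support that. The extension condition states no PGA cut-off and names no judge. Grade 4 is itself described as slight improvement and might satisfy it, in which case the incentive at the 50% line disappears. The same condition excludes PGA 0, so it also pulls against recording complete clearance. That the investigator decides is a fair inference from the PGA being a physician rating, but it is an inference.

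The order is recommended, not mandatory, and the lists may be inventories: Table 3 places Skindex-16 before the itch scales, while section 3.1 does the reverse. Nothing says patients learn their grade. An upward effect on itch is plausible but not shown.

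Two further points stand. Week 16 mCAILS, lesion count and BSA change are already secondary endpoints, so setting them beside the PGA adds presentation, not data. A masked reading of the planned 3D photographs would be a closer check, but none is planned. And the study is openly unblinded and exploratory, with no success threshold.

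These arguments limit what can be claimed. They do not remove the reason to act: the only order the protocol announces puts clinician grading first, nothing separates the Week 16 grade from the extension discussion, and correcting both costs almost nothing. Exploratory status does not excuse avoidable bias in a study whose product is an estimate.

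**Conclusion.** The point holds as a low-cost improvement to conduct, not as a demonstrated bias. Patients may rate themselves after clinician grading, and the primary-endpoint grade appears also to inform extension entry. The second part rests on two inferences: that dispensing at Week 16 marks the start of the extension, and that the PGA is what shows response. The grade 3 over grade 4 incentive needs a third, that response there means the appendix's CCR or PR. On that reading CCR+PR could be raised, while the CCR count could be lowered. Each reclassified patient is worth 8.3 points. The actual size of either effect, and the direction for itch, cannot be determined from the documents.

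**What to change.** 1. Change the recommended order in section 3.1 so that VRS, VAS, NRS, Skindex-16 and LPQOL are completed first at every visit, before examination, photographs and biopsies. Align Table 3 and the visit checklists. If any patient already has a baseline under the listed order, note the order used at each visit, because a switch would itself enter the change score.
2. Record and lock the Week 16 PGA, BSA, mCAILS and lesion count before extension entry is discussed. State in section 3.4 that primary response means CCR+PR by the appendix labels (grades 0 to 3). Locking does not remove an incentive the assessor already knows about, but it prevents revision after the discussion.
3. Optionally, list each patient's PGA response beside the Week 16 mCAILS ratio to baseline and BSA change. Present this as a consistency check, and say that these measures are also unmasked. An index-lesion score and a whole-skin grade can differ without bias.

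The cost is a reordered visit worksheet, a CRF lock step and one more table, with no added procedures or staff. Extension eligibility and dosing are not changed. The meaning of response in sections 3.3 and 5.7.3 should be reconciled with the appendix by the sponsor.
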